#### Base de datos para la Investigacion Farmacoepidemiologica en el Ambito Publico (BIFAP), Spain

BIFAP is a longitudinal population-based data source of medical patient records of the Spanish National Health Service (SNS) from 10 participating Regions throughout Spain out of the 17 Spanish Regions. Population currently included represents 36% of the total Spanish population. Spain has a SNS that provides universal access to health services through the Regional Healthcare Services. Primary care physicians (PCPs), both general practitioners and paediatricians, have a central role. They act as gatekeepers of the system and also exchange information with other levels of care to ensure the continuity of care. Most (98.9%) of the population is registered with a PCP and, in addition, most drug prescriptions are written at the primary care level. BIFAP includes a collection of databases linked at individual patient level. The main one is the Primary care Database given the central role of PCPs in the SNS. Linked, there are additional important structural databases like the medicines dispensed at community pharmacies and the patients’ hospital diagnosis at discharge. Linkage to SARS-CoV-2 diagnostics test and COVID-19 vaccination registries are also included. Additional databases are also linked for a subset of patients (hospital pharmacy, cause of death registry). BIFAP program is a non-profit program financed by the Spanish Agency of Medicines and Medical Devices (AEMPS), a government agency belonging to the Ministry of Health in collaboration with the Regional health authorities. The main use of BIFAP is for research purposes in order to evaluate the adverse and beneficial effects of drugs and drug utilization patterns in the general population under real conditions of use.

#### Clinical Data Warehouse, Bordeaux University Hospital (CDWBordeaux), France

The clinical data warehouse of the Bordeaux University Hospital comprises electronic health records on more than 2 million patients with data collection starting in 2005. The hospital complex is made up of three main sites and comprises a total of 3,041 beds (2021 figures). The database currently holds information

	D2.2.3 - Study Protocol for P3-C1-005	
	Author(s): [name] [name]	Version: V2.1
		Dissemination level: Public

about the person (demographics), visits (inpatient and outpatient), conditions and procedures (billing codes), drugs (outpatient prescriptions and inpatient orders and administrations), measurements (laboratory tests and vital signs) and dates of death (in or out-hospital death).

#### IQVIA Disease Analyser (DA) Germany, Germany

IQVIA Disease Analyzer (DA) Germany is a database of de-identified electronic medical records from specialised and general primary practices (GP) in Germany since 1992. This dataset encompasses approximately 3% of all outpatient practices within Germany, ensuring a substantial representation of the national healthcare landscape. (Rathmann, Bongaerts et al. 2018, Zappacosta, Cascarano et al. 2022) The sampling methods used for practice selection, taking into account physician's demographics, specialty focus, community size category and federal state location, was instrumental in constructing a database that accurately mirrors the diverse spectrum of healthcare providers in the country. (Rathmann, Bongaerts et al. 2018) Consequently, data within IQVIA DA Germany database has been demonstrated to be representative of general and specialised practices throughout Germany.

The database contains demographics records, basic medical data, disease diagnosis according to International Classification of Diseases, 10th revision (ICD-10), and prescription records. (Zappacosta, Cascarano et al. 2022) While the database partly records information on deaths and procedures, it currently does not support linkage with external data sources and therefore information on mortality is incomplete. Routine updates are conducted at regular intervals. The quality of data is assessed based on several criteria including completeness of information and correctness (e.g. linkage between diagnosis and prescriptions).

IQVIA DA Germany is suitable for pharmacoepidemiologic and pharmaco-economic studies as previously demonstrated. (Tanislav, Rosenbauer et al. 2022, Zappacosta, Cascarano et al. 2022, Ly, Flach et al. 2023).

### 8.3 Study Period

The study period will be from 1st January 2010 to 31st December 2022.

	D2.2.3 - Study Protocol for P3-C1-005	
	Author(s): [name] [name]	Version: V2.1
		Dissemination level: Public

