Main measure of effect:	
Incidence rates, expressed as number of individuals newly diagnosed with ILD per 100,000 person-years. Incidence rates will be calculated overall and stratified by sex, age (age category) and calendar time (year). Incidence rates will be calculated for ILD overall and for the following ILD subtypes: alveolitis/pneumonitis (excluding aspiration and infectious pneumonitis), lung fibrosis and drug induced ILD.
 
Median survival time in patients with newly diagnosed ILD stratified by sex, age-category, and calendar time. If numbers are sufficient, survival rates will not only be done for the overall group but also for the following ILD subtypes: alveolitis/pneumonitis (excluding aspiration and infectious pneumonitis), lung fibrosis and drug induced ILD.

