#### Covariates for the population-level descriptive epidemiology study (incidence and prevalence)

To characterize ILD and the most common ILD-subtypes (i) alveolitis/pneumonitis excluding aspiration and infectious pneumonitis ii) lung fibrosis and iii) drug induced ILD, the covariates for stratification in population-level descriptive epidemiology study will include age category (<18, 18-39, 40-59, 60-79 and >=80 years at index date), sex and calendar time (year) at start of follow-up.

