## 11. LIMITATIONS OF THE RESEARCH METHODS

### General limitations:

*Characterisation/Indication:* The ILD phenotype utilises codes recorded within databases and will not include imaging or test data. The accuracy and consistency of pre-defined condition recording, crucial for patient characterisation may vary across the databases included in the study. ILD is a complex condition and characterising the condition by subtype might be limited if ILD is only recorded as a general term without possibility to further categorise. Apart from CDWBordeaux, it is expected that some types of

	D2.2.3 - Study Protocol for P3-C1-005	
	Author(s): [name] [name]	Version: V2.1
	Dissemination level: Public	

medications related to ILD primarily administered in hospital will not be routinely captured within primary care databases. With regard to characterisation of individuals with ILD, previous exposure to smoking is of interest, however as smoking is not systematically recorded and thus not available in all databases, we have decided not to include smoking status as one of the covariates of interest. No linkage to hospitalisation diagnoses will be performed which may lead to an underestimation for certain types of covariates.

The analysis may suffer from small cell counts for some subgroup strata. If numbers are too low, counts will not be disclosed for governance reasons.

The incidence rate of ILD might be an underestimate of the actual incidence rate as ILD is a diagnosis made by the specialist. If information is not well transposed from secondary care to primary care, we might have an underestimate of the individuals with ILD.

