## 17. ANNEXES

**Appendix I:** List of Stand-Alone documents (e.g. lists with concept definitions (conditions & drugs), validation procedures, questionnaires etc.)

Concept IDs related to ILD were identified within the Darwin Atlas and each concept ID was reviewed to decide whether it could be included as part of ILD (table S1.A) or whether it should be excluded (Table S1.B). Amongst the included concept IDs we next differentiated between alveolitis/pneumonitis, lung fibrosis, pneumoconiosis, PAP (pulmonary alveolar proteinosis) and sarcoidosis. Amongst the subclasses, 2 broad categories could be identified namely alveolitis/pneumonitis and lung fibrosis. There are some other classes too but with presumably with limited number of individuals.

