**D2.2.3 - Study Protocol for P3-C1-005**

**Author(s):** [name] [name]

**Version:** V2.1

**Dissemination level:** Public

Concept ID	Concept Code	Concept Name	Domain	Vocabulary
4245499	60485005	Pleurobronchopneumonia	Condition	SNOMED
42600167	4.2721E+13	Pleuropneumonia	Condition	SNOMED Veterinary
4141619	266350000	Pneumococcal lobar pneumonia	Condition	SNOMED
258785	233607000	Pneumococcal pneumonia	Condition	SNOMED
4221503	420787001	Pneumococcal pneumonia associated with AIDS	Condition	SNOMED
4190647	415125002	Pneumocystosis pneumonia	Condition	SNOMED
255848	233604007	Pneumonia	Condition	SNOMED
256723	195878008	Pneumonia and influenza	Condition	SNOMED
4228277	421671002	Pneumonia associated with AIDS	Condition	SNOMED
605209	1010634002	Pneumonia caused by Acinetobacter	Condition	SNOMED
37119233	724498004	Pneumonia caused by Chlamydia pneumoniae	Condition	SNOMED
254066	233609002	Pneumonia caused by Chlamydiaceae	Condition	SNOMED
759821	1.0311E+13	Pneumonia caused by Enterobacter	Condition	SNOMED
759817	1.0291E+13	Pneumonia caused by Enterococcus	Condition	SNOMED
759816	1.0281E+13	Pneumonia caused by Enterococcus faecalis	Condition	SNOMED
759815	1.0271E+13	Pneumonia caused by Enterococcus faecium	Condition	SNOMED
37116366	733051000	Pneumonia caused by Gram positive bacteria	Condition	SNOMED
37016927	713084008	Pneumonia caused by Human coronavirus	Condition	SNOMED
36676238	772839003	Pneumonia caused by Influenza A virus	Condition	SNOMED
3661408	8.82785E+17	Pneumonia caused by SARS-CoV-2	Condition	SNOMED
759818	1.0301E+13	Pneumonia caused by Serratia	Condition	SNOMED
607087	1149093006	Pneumonia caused by vancomycin resistant Enterococcus	Condition	SNOMED
4256236	409665004	Pneumonia due to aerobic bacteria	Condition	SNOMED
257908	409664000	Pneumonia due to anaerobic bacteria	Condition	SNOMED
45757206	1.08272E+15	Pneumonia due to Ascaris	Condition	SNOMED

Concept ID	Concept Code	Concept Name	Domain	Vocabulary
46269954	1.09295E+15	Pneumonia due to Bordetella parapertussis	Condition	SNOMED
260430	51530003	Pneumonia due to Escherichia coli	Condition	SNOMED
258180	430395005	Pneumonia due to Gram negative bacteria	Condition	SNOMED
46270121	1.42931E+14	Pneumonia due to H1N1 influenza	Condition	SNOMED
40481839	442094008	Pneumonia due to Histoplasma	Condition	SNOMED
4299862	38699009	Pneumonia due to Histoplasma capsulatum	Condition	SNOMED
40482061	445096001	Pneumonia due to Human metapneumovirus	Condition	SNOMED

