**D2.2.3 - Study Protocol for P3-C1-005**

**Author(s):** [name] [name]

**Version:** V2.1

**Dissemination level:** Public

concept_id	concept_name	BIFAP	CDW Bordeaux	CPRD GOLD	IQVIA - DA Germany
4112839	Pneumonitis due to inhalation of regurgitated food			100	
4119796	Toxic pneumonitis	200			
4140472	Drug-induced pneumonitis	100			
4148529	Primary atypical interstitial pneumonia	100			
4187218	Pneumonitis due to inhaled substance	49500	12200	500	12400
4195014	Lymphoid interstitial pneumonia	100		100	
4218175	Lipoid pneumonitis			100	
4221865	Radiation pneumonitis	200			
4226132	Post-radiotherapy pneumonitis	100			
4236182	Interstitial pulmonary fibrosis of prematurity			100	
4236725	Pulmonary fibrosis due to and following radiotherapy	100			
4273378	Interstitial pneumonia	200		1300	
4306082	Aspiration pneumonitis	3100		7800	
4311555	Desquamative interstitial pneumonia	100			
4341520	Acute interstitial pneumonia	300			
36714118	Cryptogenic organizing pneumonia	800		500	
37208102	PF-ILD-progressive fibrosing interstitial lung disease				
45763749	Idiopathic interstitial pneumonia	1300			
45763750	Idiopathic pulmonary fibrosis	9100		4300	
45771019	Neuroendocrine cell hyperplasia of infancy	100			
46272927	Interstitial lung disease due to connective tissue disease			100	
46274046	Chemical pneumonitis caused by anesthesia	100	200		100

	D2.2.3 - Study Protocol for P3-C1-005	
	Author(s): [name] [name]	Version: V2.1
	Dissemination level: Public	

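### Infectious pneumonitis is excluded by code, not by patient, so COVID-19 lung disease recorded under cause-neutral codes in 2020-2022 can count as incident ILD, and the all-years results cannot separate it

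*Protocol*

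**What the plan says.** - **Period.** Section 8.3: "The study period will be from 1st January 2010 to 31st December 2022".
- **Intended exclusion.** Section 8.6.3 defines one subtype as "alveolitis/pneumonitis excluding aspiration and infectious pneumonitis". The objectives and Table 1 repeat the qualifier. It attaches to this subtype, not to lung fibrosis.
- **How it is carried out.** Appendix I sorts each concept into kept (Table S1.A) or excluded (Table S1.B). Section 11 adds: "The ILD phenotype utilises codes recorded within databases and will not include imaging or test data". The only diagnosis-based rule at patient level is that there be no earlier ILD (Table 5).
- **Excluded codes.** Table S1.B lists "Pneumonia caused by SARS-CoV-2", ARDS due to SARS-CoV-2 and an exacerbation code for SARS-CoV-2 pneumonia. It also lists unspecific codes such as pneumonia, bilateral pneumonia, atypical pneumonia and ARDS.
- **Kept codes.** Table S1.A counts pneumonitis, "interstitial pneumonia" and acute interstitial pneumonia as alveolitis/pneumonitis. It counts post-inflammatory pulmonary fibrosis as lung fibrosis.
- **Reporting.** Section 8.8.5 gives incidence for each calendar year. It reports the characterisation overall and by age group and sex, and survival by subtype, age and sex. Sections 8.1 and 8.8.3 also stratify survival by year.
- **COVID-19 data.** Section 8.2 says of BIFAP: "Linkage to SARS-CoV-2 diagnostics test and COVID-19 vaccination registries are also included". The protocol gives these data no use, and section 11 does not mention the pandemic.

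**The concern.** By excluding the SARS-CoV-2-named codes, the protocol treats COVID-19 pneumonia as something other than ILD. Yet two patients with the same illness can fall on opposite sides of the line, depending on which code was entered. One coded as SARS-CoV-2 pneumonia is not a case. One coded as pneumonitis or interstitial pneumonia is an incident case of alveolitis/pneumonitis and of ILD overall.

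Section 6 says the results should help assessors tell drug-induced ILD from cases explained by other factors. If acute infection enters the case group in the last three years, it can alter the end of the incidence trend, the comorbidity and medication profile before diagnosis, and early mortality. The tables would not show that this had happened.

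**Working it through.** There is no figure in the protocol to reproduce. The check is a comparison of the code lists and reporting rules, followed by an illustration of size.

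**1. Share of calendar time.** 2020-2022 is 3 of 13 years: 3/13 = 23%.

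**2. Size of the route (Table S2).** These are person counts without years. They are rounded (up to the next hundred, according to the note to Table 3), and persons may overlap across codes. All-kept totals are the sums of the Table S2 rows for concepts kept in Table S1.A.

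| Code | BIFAP | CDW Bordeaux | CPRD GOLD | IQVIA DA |
|---|---|---|---|---|
| Pneumonitis | 100 | 100 | 2,200 | 100 |
| Interstitial pneumonia | 200 | – | 1,300 | – |
| Acute interstitial pneumonia | 300 | – | – | – |
| Sum of the three | 600 | 100 | 3,500 | 100 |
| All kept codes | 86,000 | 16,600 | 28,000 | 28,700 |
| Share | 0.7% | 0.6% | 12.5% | 0.3% |
| Post-inflammatory fibrosis (lung fibrosis subtype) | 10,600 | – | 1,000 | – |

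These counts show where the route exists, not how many COVID-19 patients used it.

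**3. Illustration of the effect on incidence.** All inputs are assumptions: 2,000 to 6,000 recorded COVID-19 cases per 100,000 person-years (middle 4,000); 0.05% to 0.3% of them given a kept cause-neutral code (middle 0.1%); background ILD rate 20 to 40 per 100,000 person-years.

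- Extra cases per 100,000 person-years: low 2,000 × 0.0005 = 1; middle 4,000 × 0.001 = 4; high 6,000 × 0.003 = 18.
- Relative to the 2020-2022 rate, middle: 4/40 = 10% to 4/20 = 20%. Extremes: 1/40 = 2.5% and 18/20 = 90%.
- Relative to the 13-year rate, assuming equal person-time per year: 4 × 3/13 = 0.92, so 0.92/40 = 2.3% to 0.92/20 = 4.6%. Extremes: (1 × 3/13)/40 = 0.6% and (18 × 3/13)/20 = 21%.

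These percentages are for ILD overall. The same extra cases weigh more in the alveolitis/pneumonitis subtype, which is smaller, but the documents give no subtype rate.

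**4. Which outputs are exposed.**

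| Result | Split by calendar time? | Consequence |
|---|---|---|
| Annual incidence | Yes | A step is visible but not explained |
| All-years incidence | No | 2020-2022 merged with earlier years |
| Characterisation | Not in 8.8.5 | 2020-2022 merged with earlier years |
| Survival by year | Yes in 8.1 and 8.8.3, not listed in 8.8.5 | A step is visible if done; 8.8.5 needs aligning |
| All-years survival | No | 2020-2022 merged with earlier years |

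Section 8.9 rules out meta-analysis, so the merging is across years within a database.

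**The case against.** Much of the case on the other side stands.

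- **The code lists go further than infection names.** Table S1.B also removes unspecific pneumonia and ARDS codes, where much COVID-19 lung disease could be recorded. The leak is confined to the cause-neutral codes that remain.
- **Post-inflammatory fibrosis breaches no stated rule.** A reader might infer from its 10,600 persons in BIFAP that the infectious exclusion fails on a large scale. The documents do not support this. The exclusion qualifies only alveolitis/pneumonitis, the counts carry no year, and lasting fibrosis after infection may be true ILD.
- **The three codes are nearly absent from two databases.** In IQVIA DA and CDW Bordeaux they amount to at most about 100 persons. In IQVIA DA, 4 extra cases per 100,000 person-years over three years would reach 100 persons with only 100/(3 × 0.00004) = 0.83 million people under observation, while Table 3 lists 43 million subjects. The middle values therefore cannot be presumed for these codes there.
- **Calendar-year results are largely planned already.** This holds for incidence and, in sections 8.1 and 8.8.3, for survival. Section 8.1 also names calendar year among the features to describe under objective 2. Large-scale characterisation and CohortDiagnostics give partial checks.
- **A COVID-19 sensitivity analysis could be left to a statistical analysis plan.** That is fair for the details. But the protocol itself fixes the phenotype, the period, the reporting strata and the limitations. Its checklist marks sensitivity analyses as described in section 8.8, where none is described.

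What remains is that no planned output separates infection-driven recording from incident ILD.

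**Conclusion.** The point holds in a limited form. The exclusion works on codes, and nothing in the protocol identifies patients whose kept code follows COVID-19. The characterisation, the all-years incidence and the all-years survival in each database are exposed.

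A reader might infer from the 90% extreme that the overall results are badly distorted. The documents do not support that. The figure needs every assumption at its worst and refers to the 2020-2022 rate only. At the middle values the effect is 10-20% of the 2020-2022 rate and about 2-5% of the 13-year rate. The COVID-19 rate, the share given a kept code and the background rate are all assumed. Neither the true size nor the effect on survival or patient profile can be derived from the protocol. For the three named codes, the concern bears mainly on CPRD GOLD, then BIFAP. This is an inexpensive improvement that serves the stated signal-assessment purpose, not a flaw that invalidates the study.

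**What to change.** 1. Report objective 2, overall incidence and overall survival for 2010-2019 and 2020-2022 separately, beside the all-years result.
2. Align the survival strata in section 8.8.5 with the calendar-year strata in sections 8.1 and 8.8.3.
3. For 2020-2022, add a sensitivity analysis of incidence and survival. It removes index diagnoses with a COVID-19 diagnosis, or a positive test where available (for example the BIFAP linkage), in the 90 days up to the index date. Print both versions in each database used for the respective objective.
4. Add a sentence to section 11 on the pandemic years and the kept cause-neutral codes. Say there that post-inflammatory pulmonary fibrosis is kept as lung fibrosis whatever its cause, if that is intended.

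**Cost.** A calendar split on existing dates and one extra cohort definition. The split makes strata smaller, so more cells will fall under the limit of 5. The sensitivity version removes some true ILD unmasked by or following infection, which is why both versions are shown. COVID-19 ascertainment differs between databases: test linkage is described for BIFAP, while IQVIA DA has no external linkage. The size of the correction should therefore not be compared across databases.

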## 8.4 Follow-up

**Table 4.** Operational Definition of Time 0 (index date) and other primary time anchors.

[figure not shown]
Study population name(s)	Time Anchor Description (e.g. time 0)	Number of entries	Type of entry	Washout window	Care Setting 	Code Type 	Incident with respect to...
All individuals from the respective databases with at least 1 year of valid database history (not for CDWBordeaux).	Study entry date	Single entry	Incident	Anytime prior to study entry date	IP, OP, OT	SNOMED	Diagnosis of ILD
Patients newly diagnosed with ILD	Date of incident ILD	Single entry	Incident	Anytime prior to ILD	IP, OP, OT	SNOMED	Diagnosis of ILD

 IP = inpatient, OP = outpatient, ED = emergency department, OT = other, n/a = not applicable

	D2.2.3 - Study Protocol for P3-C1-005	
	Author(s): [name] [name]	Version: V2.1
	Dissemination level: Public	

To calculate incidence rates, it is important to have an appropriate denominator population and their contributed observation time. Study participants in the denominator population will begin contributing person time on the respective date of the latest of the following: 1) study start date (1st January 2010), 2) date at which they have 1 year of prior history. Participants will stop contributing person time at the earliest date of the following: 1) end of available data in each of the data sources (date of last data extraction), 2) death, 3) study end date (31st December 2022) or 4) date at which the observation period of the specific person ends (individual leaving practice or being diagnosed with ILD whatever comes first)

An example of entry and exit into the denominator population is shown in **Figure 1**. In this example, person ID 1 has already sufficient prior history before the study start date and observation period ends after the study end date, so will contribute during the complete study period. Person ID 2 and 4 enter the study only when they have sufficient prior history. Person ID 3 leaves when exiting the database (the end of observation period). Lastly, person ID 5 has two observation periods in the database. The first period contributes time from study start until end of observation period, the second starts contributing time again once sufficient prior history is reached and exits at study end date.

**Figure 1.** Included observation time for the denominator population.

For the survival analysis, patients will start follow up at ILD diagnosis index date and will be censored at the time of loss to follow-up, at end of data availability, study end date or date of death whatever comes first.

